5.4.8. Dose Reductions

Following dosing interruption or cycle delay due to toxicity, the PF-06671008 dose may need to be reduced when treatment is resumed.

No specific dose adjustments are recommended for Grade 1 treatment-related toxicity. However, investigators should always manage their patients according to their medical judgment based on the particular clinical circumstances.

Dose reduction of PF-06671008 by 1 and, if needed, 2 dose levels will be allowed depending on the type and severity of toxicity encountered. Patients enrolled in the first cohort should be discontinued from the study if more than 1 dose reduction is required. Patients requiring more than 2 (or 1 for the first cohort) dose reductions will be discontinued from the treatment and entered into the follow-up phase, unless otherwise agreed between the investigator and the sponsor. All dose modifications/adjustments must be clearly documented in the patient's source notes and CRF.

Once a dose has been reduced for a given patient, all subsequent cycles should be administered at that dose level, unless further dose reduction is required. Dose re-escalation is not allowed.

Patients experiencing a DLT may resume dosing at the next lower dose level (if applicable) once adequate recovery is achieved.

Recommended dose reductions are described in Table 3.

Table 3. Dose Reductions

Event	Action
Grade 3 or 4 non-hematologic toxicity (except CRS) considered related to PF-06671008 per investigator judgment (including persistent nausea, vomiting, diarrhea despite optimal medical therapy), excluding clinically manageable electrolyte abnormalities.	
 Hold PF-06671008 until recovery to Grade 0-1 or baseline and reduce by 1 dose level. If toxicity (Grade 3-4) reoccurs despite reduction, patient may be dose reduced again by 1 more dose level (except for the first cohort) upon recovery to Grade 0-1 or baseline. Prompt palliative and supportive measures mandated per local standard of care (eg, antiemetic). Patients who experience Grade 4 non hematologic toxicities despite intervention should be discontinued from study treatment, unless restarting treatment at reduced dose level is in the patient's best interest per investigator judgment and after consultation with Pfizer's medical monitor (eg, clear clinical benefit and no alternative treatment options).
Cytokine Release Syndrome	
 Grade 2: Hold PF-06671008 until resolved and resume at same dose level. If Grade 2 CRS reoccurs, hold PF-06671008 until resolved and consider reduction by 1 dose level based on the investigator's discretion. Grade 3: Hold PF-06671008 until resolved and consider reduction by 1 dose level based on the investigator's discretion. If Grade 3 CRS recurs despite reduction, permanently discontinue PF-06671008. Grade 4: Permanently discontinue PF-06671008.
Hematologic toxicity considered related to PF-06671008 per investigator judgment 
 Grade 4 neutropenia, ie, ANC <500 mm³ (1.0 x 10⁹/L) for more than 5 days or Febrile neutropenia, ie, fever >38.3°C (101°F) or a sustained temperature of ≥38°C (100.4°F) with ANC <1000/mm³ or Grade ≥3 neutropenic infection or Grade 4 Thrombocytopenia, ie, PLTS <25,000 mm³ (25.0 x 10⁹/L) or Grade 3 Thrombocytopenia, ie, PLTS <50,000 mm³ (50.0 x 10⁹/L) with bleeding. 	
 Hold PF-06671008 until recovery of ANC to ≥1.0 x 10⁹/L (1,000 cells/mm³) and platelets ≥75 x 10⁹/L (75,000 cells/mm³). Reduce PF-06671008 by 1 dose level. If toxicity reoccurs (grades as described on the left side) despite dose reduction, patients may either be held until recovery and continuation at same dose, or undergo further dose reduction by 1 more dose level (except for the first cohort).
Other grade 4 hematologic toxicity considered related to PF-06671008 per investigator judgment	
 Hold PF-06671008 until recovery to Grade 0-1 or baseline and reduce PF-06671008 dose by 1 dose level. If toxicity reoccurs (Grade 4) despite dose reduction, patient may either be held until recovery and continuation at same dose, or undergo further dose reduction by 1 more dose level.
No recovery of toxicities within 4 weeks of scheduled PF-06671008 infusion	
 Discontinue treatment, unless restarting treatment at reduced dose level is in the patient's best interest per investigator judgment and after consultation with Pfizer's medical monitor (eg, clear clinical benefit and no alternative treatment options).

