3.3. DLT Definition

Severity of adverse events will be graded according to CTCAE version 4.03 ([Appendix 6](#)). For the purpose of dose escalation, any of the following adverse events occurring in the first cycle of treatment (21 days after the first dose) will be classified as DLTs, unless there is a clear alternative explanation (eg, related to underlying disease/progression):

Hematologic:

- Grade 4 neutropenia lasting ≥ 5 days;
- Febrile neutropenia defined as an absolute neutrophil count (ANC) $<1.0 \times 10^9/L$ with a single temperature of $>38.3^{\circ}\text{C}$, or 101°F , or a sustained temperature of $\geq 38^{\circ}\text{C}$, or 100.4°F , for more than one hour;
- Grade ≥ 3 neutropenia with infection;
- Grade 3 thrombocytopenia with Grade ≥ 2 bleeding;

- Grade 4 thrombocytopenia.

Non-hematologic:

- Grade 4 toxicities (not attributed to CRS) that are considered clinically significant;
- Grade 3 toxicities (not attributed to CRS) that are considered clinically significant despite maximal supportive care (eg, nausea, vomiting, diarrhea, easily corrected electrolyte abnormalities) that last >72 hours;
- Grade ≥ 3 CRS considered not to be due to an IRR, allergic reaction or anaphylaxis, except those i) not maximally treated or ii) events that are maximally treated, (eg, including the use of tocilizumab and/or vasopressors), and resolve to \leq Grade 2 within 72 hours;
- Delay by more than 2 weeks in receiving the next scheduled dose due to persisting treatment related toxicities.

In addition, clinically important or persistent toxicities that are not included in the above criteria may be considered a DLT following review by the sponsor and the investigators.

Grade 3 infusion reaction, allergic reaction or anaphylaxis will not be considered as DLTs but may be a reason for study discontinuation and should be reviewed with the sponsor.

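### Protocol Section 5.4.8 permits re-dosing one level down after any DLT, but its Table 3 ends treatment for good after Grade 4 CRS, which can itself be a DLT, and no precedence is stated

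*Protocol*

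**What the plan says.** Three pieces of protocol text bear on the same patient.

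- **Section 3.3, DLT Definition.** Among the non-hematologic DLTs in the first cycle is Grade 3 or higher "CRS considered not to be due to an IRR, allergic reaction or anaphylaxis, except those i) not maximally treated". The second exception covers events that were maximally treated and came down to Grade 2 or lower within 72 hours.
- **Section 5.4.8, body text.** "Patients experiencing a DLT may resume dosing at the next lower dose level (if applicable) once adequate recovery is achieved". The next sentence introduces the table: "Recommended dose reductions are described in Table 3".
- **Section 5.4.8, Table 3, CRS row.** For Grade 4: "Grade 4: Permanently discontinue PF-06671008". For Grade 3: "Grade 3: Hold PF-06671008 until resolved and consider reduction by 1 dose level based on the investigator's discretion", followed by "If Grade 3 CRS recurs despite reduction, permanently discontinue PF-06671008".

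The general non-hematologic row of Table 3 does not cover CRS. It is limited to "Grade 3 or 4 non-hematologic toxicity (except CRS) considered related to PF-06671008 per investigator judgment". The SAP contains no re-dosing rule.

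**The concern.** The DLT sentence in Section 5.4.8 is written for every patient with a DLT and makes no distinction by type or grade. The CRS row of Table 3 is written for every patient with CRS and makes no distinction by whether the event was a DLT. A CRS event that meets the DLT definition falls under both, and the two do not agree.

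At stake is consistent handling of a patient who has had a severe, prolonged reaction. A site that follows the body text may restart after recovery. A site that follows the table stops for good. Each can point to Section 5.4.8 as its authority, and a monitor checking compliance would find support there for either course.

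**Working it through.** There is no figure in the plan to reproduce and no formula to apply. The check is a comparison of texts.

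**Step 1. Can CRS be a DLT, and at which grades?** Section 3.3 starts at Grade 3 and sets no upper grade. The two exceptions depend on how the event was treated and how fast it resolved, so Grade 4 events are not excluded as such. Grade 3 and Grade 4 CRS can both be DLTs.

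**Step 2. Which rows of Table 3 give a CRS-specific action?** The general non-hematologic row excludes CRS, so the CRS row is the one to read. That general row lets a Grade 4 patient restart at a reduced level where this is judged to be in the patient's best interest, after consultation with the sponsor's medical monitor. The Grade 4 CRS line has no such exception.

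**Step 3. Set the instructions side by side.**

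| Event | DLT sentence, Section 5.4.8 | CRS row, Table 3 | Result |
|---|---|---|---|
| Grade 4 CRS, DLT | May restart one level down after recovery | Permanent stop | Direct conflict |
| Grade 3 CRS, DLT, first occurrence | May restart one level down after recovery | Hold until resolved; reduction at the investigator's discretion, so the same dose is possible | Differs only if no reduction is made |
| Grade 4 CRS, not a DLT (maximally treated, Grade 2 or lower within 72 hours) | Does not apply | Permanent stop | No conflict |

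**Step 4. Look for a rule that settles it.**

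- Section 5.4.6 bases the need for a reduction on the Dose Reductions section, which is where the conflict sits. Its allowance for a different agreement with the sponsor concerns the need for a reduction, not a permanent stop.
- Section 5.4.7 sets recovery conditions and then also refers to the Dose Reductions section.
- Section 5.4.8 gives no order between its body text and its table.
- The SAP is silent.

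**Step 5. Consequence of a literal reading.** Rows 1 and 3 of the table come out inverted. A Grade 4 CRS that settles quickly under maximal treatment is not a DLT and meets only the permanent stop. A Grade 4 CRS that persists is a DLT and gains a permission to restart that the milder course lacks. This suggests that the DLT sentence was not drafted with Grade 4 CRS in mind, but the text does not say so.

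**The case against.** The best defence is that the specific rule overrides the general one. The DLT sentence is permissive and qualified, and it leads straight into Table 3. Earlier in the section the protocol says: "Dose reduction of PF-06671008 by 1 and, if needed, 2 dose levels will be allowed depending on the type and severity of toxicity encountered". Table 3 takes CRS out of the general row and gives it graded instructions of its own. On this reading, a site that stops after Grade 4 CRS breaches neither text, and neither does a site that goes down one level after Grade 3 CRS.

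This is a plausible reading and many sites would probably adopt it. It does not remove the problem. The protocol never states that the table overrides the text, and it calls the table's reductions recommended, which leaves room for the opposite reading. The qualifier on the DLT sentence most naturally concerns whether a lower level exists. A site that restarts a patient after a Grade 4 CRS DLT complies with one instruction and breaks the other.

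For Grade 3 much of the defence stands. The reduction that Table 3 asks the investigator to consider is the same single step that the DLT sentence permits, so the texts part only when the investigator keeps the dose unchanged.

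A reader might infer more than the documents support:

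- **That every CRS DLT is affected to the same degree, with a calculable dose difference between sites.** For Grade 3 the texts agree whenever a reduction is made. The spacing of the dose levels describes the grid, not an effect of this inconsistency.
- **That Grade 3 CRS recurring without a prior reduction has no instruction.** The Grade 3 line is not limited to a first occurrence and can be read as applying again.
- **That CRS drives the DLT count.** Section 3.3 lists many DLT criteria and excludes CRS that is not maximally treated or that settles quickly. Nothing in the documents shows which criterion will dominate.
- **That the RP2D would be distorted.** The dose-reduction trigger in Section 3.6 is an example tied to the expansion part, whereas DLTs are classified for dose escalation. The link is indirect at most.

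**Conclusion.** The inconsistency is real. For Grade 4 CRS that meets the DLT definition, Section 5.4.8 contains a permission to restart and a permanent stop, with no stated precedence. For a Grade 3 CRS DLT there is a lesser divergence, confined to the case where the investigator does not reduce the dose.

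Its size is that of a wording conflict on patient safety. A DLT is counted because the event occurred, whatever happens to dosing afterwards, so no mTPI decision rule and no sample size changes. How often a Grade 4 CRS DLT would arise cannot be estimated from the documents.

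The conclusion rests on two assumptions: that the DLT sentence applies to all DLTs, as worded, and that no precedence rule stands in the text that is blacked out at the start of Section 5.4. It should be corrected because it concerns re-exposure after a life-threatening grade of toxicity and is easy to repair.

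**What to change.** Reconcile the DLT sentence in Section 5.4.8 with the CRS row of Table 3. State explicitly which text governs when a CRS event is also a DLT, once for Grade 4 and once for Grade 3. A cross-reference in the DLT sentence, with matching wording in the CRS row, would be enough. Which rule applies is for the sponsor and investigators to decide, and no view is taken here.

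The cost is about a sentence in the body text and, if needed, a line in the table, made through a protocol amendment. It needs no extra patients, no extra data and no change to the SAP.

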3.2.2. Criteria for Dose Escalation

The study has been designed to establish the MTD defined as the dose that yields approximately 27.5% probability of DLT and considers equivalent doses that yield probability of DLT in the interval (Equivalence Interval) 22.5% to 32.5%.

Typically patients will be enrolled in cohorts of 2 to 4, but patients could be initially enrolled in cohorts of 1-2 for the lower doses (see section [Dose Escalation Phase \(Part 1\)](#)). The initial 2-4 patients to be included in a cohort will be open to any of the tumor types outlined in [Appendix 2](#). When required to expand a cohort for further evaluation of the MTD, enrollment of patients may be limited to those with NSCLC, SCCHN, CRC or TNBC.

For IV administration cohorts, initial dose levels are provided in [Table 1](#) and will be followed if no DLTs are observed; intermediate doses may be evaluated based on clinical findings. Subsequent maximum dose increases will be a maximum of 2-fold (100%) if no DLTs are observed. For SC administration cohorts, during the initial dose escalation levels, maximum dose increases will be up to 3-fold if no DLTs or safety events that are approaching the limit of tolerability are observed. The initial dose to be evaluated for SC administration will be equal to the dose level selected as the IV Dose Prime. The evaluation of the IV and SC routes of administration will proceed through dose escalation independently according to the mTPI method. Once the first DLT is observed, the maximum increase would follow a modified Fibonacci series in case of dose escalation (ie, 67%, 50%, 33%, etc.). Patients will be assigned to a dose that is closest to the current MTD prediction based on the mTPI method. The mTPI method relies upon a statistical probability algorithm, calculated using all patients treated in prior and current cohorts at the same dose level to determine (Decision Rules) where future cohorts should involve dose escalation, no change in dose, or dose de-escalation as presented in [Table 2](#) (see also Section [Statistical Methods and Properties](#)).

Table 1. Dose Escalation Levels for IV Administration

Dose Level	Dose (ng/kg)
1 (Starting Dose)	1.5
2	7.5
3	20
4	50
5	100
6	200
7	300
8	400

* Intermediate doses may be evaluated based on clinical findings (eg, a dose between 20 and 50 ng/kg).

Table 2. Decision Rules

Number of Patients Having DLT	Number of Patient Treated at a Dose Level										

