5.4.7. Dose Delays

Re-treatment following treatment interruption for treatment-related toxicity or at the start of any new cycle may not occur until all of the following parameters have been met:

- ANC $\geq 1,000/\text{mm}^3$.
- Platelets count $\geq 50,000/\text{mm}^3$.
- Non-hematologic toxicities have returned to baseline or Grade ≤ 1 severity (or, at the investigator discretion, Grade ≤ 2 if not considered a safety risk for the patient).

If a treatment delay results from worsening of hematologic or biochemical parameters, the frequency of relevant blood tests should be increased as clinically indicated.

If these conditions are met within 14 days of treatment interruption or cycle delay, PF-06671008 may be resumed. Refer to Section Dose Reductions for AEs requiring dose reduction at the time of treatment resumption.

If treatment interruption due to toxicity exceeds 14 days, treatment with this agent should be permanently discontinued.

The day when the patient receives their 4th dose of study drug will be counted as Day 1 of the next cycle. Subsequent cycles will be 21 days in length regardless of treatment delays.

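### Table 3 gives the wrong SI value for the Grade 4 neutropenia dose-reduction trigger: an ANC of 500/mm³ is 0.5 × 10⁹/L, not 1.0 × 10⁹/L

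*Protocol*

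**What the plan says.** Table 3 (protocol section 5.4.8) has a row for haematologic toxicity judged related to study drug. Its first trigger is "Grade 4 neutropenia, ie, ANC <500 mm³ (1.0 x 10⁹/L) for more than 5 days". Other triggers in the same cell are febrile neutropenia, with its own ANC cut-off of <1000/mm³, neutropenic infection of Grade 3 or higher, "Grade 4 Thrombocytopenia, ie, PLTS <25,000 mm³ (25.0 x 10⁹/L", and Grade 3 thrombocytopenia with bleeding.

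The action column begins "Hold PF-06671008 until recovery of ANC to ≥1.0 x 10⁹/L (1,000 cells/mm³", adds the platelet condition "platelets ≥75 x 10⁹/L (75,000 cells/mm³", and then calls for a reduction of one dose level.

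The text above the table adds "Dose re-escalation is not allowed" and "Patients requiring more than 2 (or 1 for the first cohort) dose reductions will be discontinued from the treatment", with an exception where the investigator and sponsor agree otherwise. Section 5.4.7 says "Re-treatment following treatment interruption for treatment-related toxicity or at the start of any new cycle may not occur until" a list of conditions is met, the first being an ANC of at least 1,000/mm³.

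**The concern.** The conventional and SI figures in the trigger define different thresholds. A patient with an ANC of, say, 0.7 × 10⁹/L is above the first and below the second.

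Haematology is analysed locally, so a site may work in either unit. This is also the only place in the protocol that puts a number on Grade 4 neutropenia. The DLT definition in section 3.3 names the grade alone, and the CTCAE is supplied through the Study Manual.

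A site that acted on the SI figure could take a patient down one dose level when neither the Grade 4 label nor the <500 figure calls for it. The patient would then stay at the lower dose, with one fewer reduction in hand.

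**Working it through.** **Conversion.** 1 L = 10⁶ mm³, so a count per mm³ × 10⁶ ÷ 10⁹ gives the value in 10⁹/L. Applied to the paired thresholds in Table 3 and in the inclusion criteria (section 4.1):

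| Threshold | Per mm³ | Computed, 10⁹/L | Printed, 10⁹/L | Agrees |
|---|---|---|---|---|
| ANC, inclusion | 1,500 | 1.5 | 1.5 | yes |
| Platelets, inclusion | 100,000 | 100 | 100 | yes |
| ANC recovery, Table 3 | 1,000 | 1.0 | 1.0 | yes |
| Platelet recovery, Table 3 | 75,000 | 75 | 75 | yes |
| Grade 4 thrombocytopenia, Table 3 | 25,000 | 25.0 | 25.0 | yes |
| Grade 3 thrombocytopenia, Table 3 | 50,000 | 50.0 | 50.0 | yes |
| Grade 4 neutropenia, Table 3 | 500 | 0.5 | 1.0 | **no** |

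In reverse, 1.0 × 10⁹/L is 1,000/mm³, and 1,000 ÷ 500 = 2. Six of the seven pairs agree and only the neutropenia trigger fails.

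**Which figure is right.** The arithmetic shows only that the pair is inconsistent. Three features of the text point to 500/mm³:

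- The trigger is labelled Grade 4.
- The conventional figure is stated first, as the definition.
- The same cell gives febrile neutropenia a separate, higher cut-off of <1000/mm³, which section 3.3 writes as <1.0 × 10⁹/L.

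The documents do not reproduce the CTCAE grade limits, so the conclusion rests on these features.

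**Who is affected.** The two readings differ for ANC from 0.5 to below 1.0 × 10⁹/L lasting more than 5 days, drug-related, without fever or infection. Patients with febrile neutropenia or neutropenic infection meet the row on either reading. The hold hardly changes, because section 5.4.7 bars re-treatment below 1,000/mm³ in any case. The difference lies in the dose reduction.

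**Size of one mistaken reduction.** Assume that reduction steps follow the IV levels in section 3.2.2, Table 1. The proportional loss is (higher − lower) ÷ higher:

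| Step, ng/kg | Loss |
|---|---|
| 400 to 300 | 25% |
| 300 to 200 | 33% |
| 200 to 100 | 50% |
| 100 to 50 | 50% |
| 50 to 20 | 60% |
| 20 to 7.5 | 62.5% |
| 7.5 to 1.5 | 80% |

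For the first cohort, section 9.2 provides a step-down dose of 1.0 ng/kg: (1.5 − 1.0) ÷ 1.5 = 33%.

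**Where a mistaken reduction would be counted.** SAP section 6.1 tabulates patients with dose reductions. Protocol section 3.6 gives more than 25% of expansion patients needing a reduction for toxicity as an example of when a lower RP2D may be considered. With 10 to 20 patients per indication, one patient is 1/20 = 5 to 1/10 = 10 percentage points of an indication. Over all three indications (30 to 60 patients) one patient is 1/60 = 1.7 to 1/30 = 3.3 points. Section 3.6 does not say which denominator applies.

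**The case against.** The best reply is that the line largely corrects itself. The grade and the conventional value come first, the wrong figure is a gloss in parentheses, and the action column of the same row pairs 1.0 × 10⁹/L with 1,000 cells/mm³. A site would have to overlook all of these to be misled.

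The consequence is also softened by discretion elsewhere. Section 5.4.6 lets the investigator and sponsor agree not to apply the reduction criteria, and section 5.4.8 does the same for discontinuation after the permitted reductions. Table 3 is introduced as recommendations, and after a recurrence the row allows the same dose to continue. The group concerned is narrow, and the error leads to too low a dose rather than to added toxicity. The percentage range is only the spacing of the IV levels. Its upper end belongs to the two lowest doses, intermediate doses are permitted, and it does not carry over to SC dosing.

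These points are fair, and they limit how often the error would matter and how far the percentages can be pressed. They do not make the printed figure right. It is a decision threshold in a dosing instruction, and the fact that its own row contradicts it is a reason to correct it.

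**Conclusion.** The concern holds. The SI figure is wrong by a factor of two, and no reading of the units reconciles it with 500/mm³. That 0.5 × 10⁹/L was intended is an inference from the line itself, and a strong one.

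The practical effect is confined to dose modification. A site that relied on the SI figure could make an unneeded, irreversible one-level reduction in a narrow group of patients. On the Table 1 IV steps that costs 25% to 80% of the dose, and 50% from 200 or 100 ng/kg. How many patients this would reach cannot be estimated, since the documents give neither the frequency of such neutropenia nor the units that sites use.

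The DLT criterion cites the grade without a number, so DLT classification, the mTPI decisions and the sample size are unaffected. No planned analysis uses the threshold itself, although any reduction made in error would enter the counts of dose reductions.

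**What to change.** In Table 3, change the trigger to read: Grade 4 neutropenia, ie, ANC <500/mm³ (<0.5 × 10⁹/L) for more than 5 days. This also restores the missing slash in the conventional unit and the inequality sign in the SI value. The cost is one figure in the next amendment. A short note to sites could cover the time until then. Nothing in the SAP needs to change.
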